### 8.0 TOXICITIES TO BE MONITORED AND DOSE MODIFICATIONS

#### 8.1 NCI Common Terminology Criteria for Adverse Events

This study will utilize the CTCAE Version 5.0 for toxicity and serious adverse event reporting. A copy of the CTCAE Version 5.0 can be downloaded from the CTEP home page https://ctep.cancer.gov. All appropriate treatment areas should have access to a copy of the CTCAE Version 5.0.

8.2 Supportive Care

Blood product transfusion, intravenous albumin, intravenous fluids and electrolyte replacement, antiemetics, antidiarrheal medication, g-csf, anti- hypersensitivity medications are all allowable as per institutional standards and Section 3 of the protocol.

- 8.3 Dose Delays
  - a. No dose reduction is authorized for isatuximab.
  - b. Cycle delay up to 14 days is allowed, as indicated in Table 1 below.

Any additional delay (beyond 14 days) must be determined in consultation with the Study Chair(s), and documented via email to: [contact] and [contact]. The decision to continue treatment will be based on potential for continued clinical benefit, as determined jointly by the treating physician(s) and Study Chair(s). Treatment may not be delayed for any reason for more than 42 consecutive days.

c. Within a cycle, an isatuximab administration can be delayed for up to +/-3 days. If the dose cannot be administered within +/- 3 days, the isatuximab dose will be omitted. If one dose of isatuximab is administered within these windows, the interval between the next infusions should be maintained to 1 week or 2 weeks respectively

Only 1 omission per cycle is permitted. Further omissions must be discussed on a case by case basis with the Study Chair, documented by email to: [contact] and [contact].

d. If a patient experiences several AEs and there are conflicting recommendations, follow the most conservative dose delay.

Treatment-related Adverse Event	Grade of Event	Management for Isatuximab	
Neutropenia	≤ Grade 1	No change.	
	Grade 2	No change.	
	Grade 3 Hold isatuximab until ≤ Grade 3		
	Grade 4 Off protocol therapy.		
	 G-CSF may be used per treating physician discretion and institutional guidelines. See Section 8.4 .		
Anemia 	≤ Grade 1	No change.	
	Grade 2	Hold isatuximab until < Grade 2.	
	Grade 3	Hold isatuximab until < Grade 2.	

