#### e. Soft Tissue / Lymph Nodes:

To be assessed clinically; however, if imaging was used at baseline it is suggested that follow-up assessments also be by imaging.

f. Liver:

Imaging (CT, US or MRI) to document size of liver, serum alkaline phosphatase (ALP)  $% \left( ALP\right) =0$ 

g. Gastrointestinal:

Clinical assessment of GI bleeding, diarrhea; 24-hour fecal fat test

h. Serum Chemistry:

Must include: sodium, potassium, chloride, bicarbonate, blood urea nitrogen, creatinine/ CrCl, glucose, total protein, albumin, calcium, total bilirubin, alkaline phosphatase, uric acid, and SGOT/AST and SGPT/ALT.

- 7.5 Criteria for Removal from Protocol Treatment
  - a. Hematologic progression of disease or symptomatic deterioration (as defined in Sections 10.2 and 10.7). Organ progression (as defined in Section 10.4) in the absence of hematologic progression does not necessitate removal from treatment.
  - b. Unacceptable toxicity.
  - c. Treatment delay >14 days, unless approved by the Study Chair, as indicated in Section 8.3b. Treatment must not be delayed for any reason > 42 days. For treatment delay of >14 days, see Section 8.3b.
  - d. The patients may withdraw from the study at any time for any reason.
  - e. 24 cycles of treatment completed as planned.
  - f. Development of overt myeloma.
- 7.6 Discontinuation of Treatment

All reasons for discontinuation of treatment must be documented in the Off Treatment Notice.

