#### Table 1: Dose Delays for Isatuximab

Treatment-related Adverse Event	Grade of Event	Management for Isatuximab	
	Grade 4	Off protocol therapy.	
	
 
Dose delay is not required for anemia, unless deemed necessary by the treating physician. Transfusions and/or erythrocyte stimulating agents are allowable.
 
		
All other events	≤ Grade 1	No change.	
	Grade 2	Hold isatuximab until < Grade 2 OR patient returns to baseline (where patient had a predetermined abnormal baseline).	
	Grade 3	Hold isatuximab until < Grade 2 OR patient returns to baseline (where patient had a predetermined abnormal baseline).	
	Grade 4	Off protocol therapy.	

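### The hold for Grade 3 neutropenia in Table 1 ends at a condition that a Grade 3 event already meets, so no recovery is required before the next dose

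*Combined protocol and SAP*

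**What the plan says.** Section 8.3 authorises no dose reduction for isatuximab (8.3a), so toxicity is managed by holding, omitting or stopping. Table 1 gives the rules for treatment-related events.

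- **Neutropenia.** Dosing is unchanged up to Grade 2. At Grade 3 the entry is "Hold isatuximab until ≤ Grade 3". The next row reads "Grade 4 Off protocol therapy". The footnote adds that "G-CSF may be used per treating physician discretion and institutional guidelines"; it sets no recovery level.
- **Anemia, Grades 2 and 3.** "Hold isatuximab until < Grade 2". A footnote makes this hold discretionary.
- **All other events, Grades 2 and 3.** "Hold isatuximab until < Grade 2 OR patient returns to baseline", the second limb being for patients whose baseline was already abnormal.

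The timing rules around the table are these. Section 8.3b: "Cycle delay up to 14 days is allowed, as indicated in Table 1 below". Section 8.3c, for doses within a cycle: "If the dose cannot be administered within +/- 3 days, the isatuximab dose will be omitted". Section 7.5c lists as a criterion for removal from treatment: "Treatment delay >14 days, unless approved by the Study Chair". No delay may exceed 42 days.

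**The concern.** A hold rule needs a trigger and a release. Here the trigger is Grade 3 and the release is Grade 3 or lower, so the trigger satisfies the release. The entry says to hold but requires nothing to improve before dosing resumes.

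Two sites could therefore act differently on the same blood count. One that applies the text literally could dose through Grade 3 neutropenia; one that infers the intent would wait for Grade 2. The resume point also determines how the dose is classified: given on time, omitted because it falls outside the 3-day window, or part of a delay long enough to need Study Chair approval. Because dose reduction is not available, the hold is the only dosing response the protocol offers at this grade.

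**Working it through.** There is no stated figure to reproduce. The check is whether each hold entry can bind, followed by a search for a threshold elsewhere.

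**Step 1. Test each hold entry in Table 1 at onset.**

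| Entry | Grade at trigger | Release condition | Met at onset? |
|---|---|---|---|
| Neutropenia, Grade 3 | 3 | ≤ 3 | Yes (3 ≤ 3) |
| Anemia, Grade 2 | 2 | < 2 | No |
| Anemia, Grade 3 | 3 | < 2 | No |
| All other events, Grade 2 | 2 | < 2, or return to baseline | No |
| All other events, Grade 3 | 3 | < 2, or return to baseline | No |

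For the last two rows, a new or worsened event has by definition not returned to baseline. One entry of five is met at onset.

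**Step 2. Could the condition describe recovery from something worse?** The only higher non-fatal grade is 4, and Grade 4 neutropenia ends protocol therapy. The condition can therefore never prolong a hold.

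**Step 3. Does another section supply the threshold?**

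- Section 8.3b and Section 7.5c set maximum delays (14 days, or up to 42 with Study Chair agreement) and no minimum.
- Section 8.3d, which prefers the most conservative delay, applies only when several adverse events give conflicting instructions.
- The row for all other events does not cover neutropenia, which has its own rows.
- Section 11.5 counts as a run-in event a Grade 4 neutropenia that fails to fall below Grade 3 within 10 days. This defines a monitoring event, not a dosing rule, but it shows the protocol using below Grade 3 as a neutropenia recovery level.

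No section gives a neutropenia level at which isatuximab may resume.

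**Step 4. Which threshold fits?** With < Grade 3 (equivalently ≤ Grade 2), a patient at Grade 3 does not meet the release condition, and dosing resumes at Grade 2, where the same table leaves dosing unchanged. With < Grade 2, as in the other rows, drug would be withheld at Grade 2 in a recovering patient but not in a patient who never went higher. Only < Grade 3 is consistent with the rest of the neutropenia block.

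**Step 5. How often might the entry apply?** This is illustrative only. Section 3.1c appears to list neutropenia in the column for events above 20%, without a grade split. Inputs: 20% taken as the any-grade rate, 35 evaluable patients (Section 11.1), and an assumed Grade 3 share of 10% to 50%.

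- Any grade: 0.20 × 35 = 7.0 patients.
- Share 10%: rate 0.20 × 0.10 = 0.02; expected 0.02 × 35 = 0.7; P(at least one) = 1 − 0.98^35 = 0.507.
- Share 50%: rate 0.20 × 0.50 = 0.10; expected 0.10 × 35 = 3.5; P(at least one) = 1 − 0.90^35 = 0.975.

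**The case against.** The strongest objection is to the source. The row's grade and management cells ran together when the PDF was read, so a misread symbol is possible, and a reading fault is not an error in the plan. This stands as a caveat: the PDF should be checked first. It does not dispose of the point, because ≤ and < are kept distinct elsewhere in the same table.

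Second, the intent is fairly clear. With no change at Grade 2, a hold at Grade 3 and removal at Grade 4, a sensible investigator would resume at Grade 2, and to dose at Grade 3 is to treat an instruction to hold as empty. Section 11.5 supports that reading. This is fair and limits the practical risk, but a dosing rule should state its threshold rather than leave it to be deduced.

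Third, the harm is bounded. A blood count is required on each dosing day or within the 3 days before it (Section 9.0, footnote C), G-CSF is allowed, Grade 4 stops treatment, and Section 7.0 directs dosing questions to study contacts. All of this stands.

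Fourth, the frequency range is soft. The Grade 3 share is assumed, the 20% is read from a broken table, and the most common events listed in Section 2.4 for the earlier isatuximab study do not name neutropenia, although those lists may leave out laboratory findings. This also stands, so the range should be given little weight.

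Finally, two of the four comparison entries (anemia) are discretionary under their footnote, which softens the one-in-five contrast. The logical defect in the neutropenia row does not depend on that contrast.

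**Conclusion.** The concern holds. As written, the Grade 3 neutropenia entry imposes a hold with no required recovery and a minimum length of zero days, and nothing else in the protocol supplies the missing threshold. It is a wording error in an operative safety rule, worth correcting but limited in consequence: the two-stage design, significance level, power and response denominator are untouched.

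The conclusion rests on the symbol being correctly read from the PDF. The estimate of 0.7 to 3.5 affected patients, with a 51% to 97% chance of at least one, rests on an assumed Grade 3 share and an insecure any-grade rate; the conclusion does not depend on it.

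**What to change.** Check the symbol in the source PDF. If it is as extracted, change the Grade 3 neutropenia entry so that isatuximab is held until neutropenia is below Grade 3 (Grade 2 or better), and notify sites. This agrees with the Grade 2 row and with the recovery level in Section 11.5.

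The cost is one symbol in one table cell plus the site notice, with no change to design, sample size or analysis. As a separate editorial matter, the anemia Grade 2 and 3 rows could be reworded in the same revision to match their footnote, which already makes that hold discretionary.

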#### Table 1: Dose Delays for Isatuximab

Treatment-related Adverse Event	Grade of Event	Management for Isatuximab	
	Grade 4	Off protocol therapy.	
	
 
Dose delay is not required for anemia, unless deemed necessary by the treating physician. Transfusions and/or erythrocyte stimulating agents are allowable.
 
		
All other events	≤ Grade 1	No change.	
	Grade 2	Hold isatuximab until < Grade 2 OR patient returns to baseline (where patient had a predetermined abnormal baseline).	
	Grade 3	Hold isatuximab until < Grade 2 OR patient returns to baseline (where patient had a predetermined abnormal baseline).	
	Grade 4	Off protocol therapy.	

#### 8.4 White Blood Cell Growth Factors

If used, white blood cell growth factors, including biosimilars, must be used per ASCO guidelines http://jco.ascopubs.org/content/24/19/3187.full and NCCN Guidelines® Myeloid Growth Factors http://www.nccn.org/professionals/physician\_gls/pdf/myeloid\_growth.pdf.

## 8.5 Guidelines for the Management of Infusion Reactions (IRs)

Patients should routinely receive premedications prior to isatuximab infusion to reduce the risk and severity of IARs commonly observed with monoclonal antibodies. Infusion associated reactions are defined as AEs related to isatuximab with onset typically within 24 hours from the start of the infusion.

Patients presenting Grade 2 IAR(s) with infusion interruption may subsequently resume isatuximab at half of the initial infusion rate under close monitoring and supportive care as needed. These patients must be informed of the potential risk of recurrent infusion reactions upon rechallenge. For further infusions, patients may receive additional premedication per the judgment of the Investigator. Additional recommended premedications include diphenhydramine 25 mg IV (or equivalent) and methylprednisolone 100 mg IV.

Once a Grade 2 IAR leading to interruption has improved to Grade  $\leq 1$ , the infusion may be restarted at half the original infusion rate. If symptoms do not recur after 30 minutes, the infusion rate may be increased in 50 mg/hour increments every 30 minutes, to a maximum of 400 mg/hour.

Patients presenting Grade 3 or 4 isatuximab IAR(s) must have isatuximab permanently discontinued and appropriate supportive therapy should be administered. The IAR(s) and the therapy administered must be documented in the eCRF.

CTCAE Version 5.0 criteria definition	Intervention recommendation		
Mild (Grade 1) Infusion interruption or intervention not indicated	Continuation of isatuximab infusion per the judgment of the Investigator following close direct monitoring of the patient's clinical status. Isatuximab infusion may be stopped at any time if deemed necessary. If stopped, IAR will be classified as Grade 2 as per CTCAE Version 5.0.		
Moderate (Grade 2) Therapy or infusion interruption indicated, but responds promptly to symptomatic treatment (eg, antihistamines, NSAIDs, narcotics, IV fluids); prophylactic medications indicated for ≤ 24 hours	Stop isatuximab infusion. Give additional premedication with diphenhydramine 25 mg IV (or equivalent) and/or methylprednisolone 100 mg IV (or equivalent) as needed. Isatuximab may be resumed only after patient recovery, with slower infusion rate and with close monitoring.		
Severe or life-threatening (Grade 3 or 4) Grade 3: prolonged (eg, not rapidly responsive to symptomatic medication and/or brief interruption of infusion); recurrence of symptoms following initial improvement; hospitalization indicated for clinical sequelae Grade 4: life-threatening consequences; urgent intervention indicated			
Note: infusion should be completed within 16 hours from the end of infusion preparation or a new infusion should be prepared with the remaining dose to be administered the same day. Abbreviations: AE = adverse event; IAR = infusion associated reaction; IV = intravenous; NCI-CTCAE = National Cancer Institute Common Terminology Criteria for Adverse Events; NSAIDs = nonsteroidal anti-inflammatory drugs.			

Table 2 - Management of infusion associated reactions

8.7 Adverse Event Reporting

Toxicities (including suspected reactions) that meet the expedited reporting criteria as outlined in Section 16.0 of the protocol must be reported to the Operations Office, Study Chair and NCI via CTEP-AERS, and to the IRB per local IRB requirements.

## 9.0 STUDY CALENDAR

	PRE-STUDY (w/in 28 days		C	Cycle Length = 28 (+/- 3 days)	days		Off TX	Post Progression FU			
REQUIRED STUDIES	registration, unless otherwise noted)	Cycle 1	Cycle 2	Cycle 3	Cycle 4	Subsequent Cycles up to 24 Cycles	Pre- Progression FU				
PHYSICAL											
History and Physical Exam O	х	Х	Х	Х	Х	Х					
Height	х										
Weight	x	х	Х	х	х	х					
Performance Status	X	Х	Х	х	Х	Х					
Toxicity Notation		X (Days 1, 8, 15, 22)	X (Days 1, 15)	X (Days 1, 15)	X (Days 1, 15)	X (Days 1, 15)	XQ	Xq			
NYHA Assessment	х	х	х	х	х	х	х				
Vital Signs N	х	x	х	х	х	х	x				
Clinical autonomic neurologic evaluation A, H	x	X (every 2 cycles, +/- 7 days)		X (every 2 cycles, +/- 7 days)		X (every 2 cycles, +/- 7 days)	X (every 6 months, +/- 21 days)				
Clinical peripheral neurologic evaluation A, H, K	х	X (every 2 cycles, +/- 7 days)		X (every 2 cycles, +/- 7 days)		X (every 2 cycles, +/- 7 days)	X (every 6 months, +/- 21 days)				
Clinical GI evaluation A, H, K	х	X (every 2 cycles, +/- 7 days)		X (every 2 cycles, +/- 7 days)		X (every 2 cycles, +/- 7 days)	X (every 6 months, +/- 21 days)				
LABORATORY											
Type and screen and blood bank notification E	x										
CBC w/ differential, Platelets C	х	X (Days 1, 8, 15, 22)	X (Days 1, 15)	X (Days 1, 15)	X (Days 1, 15)	X (Days 1, 15)					
Serum Chemistry C, J, K	х	X (Days 1, 8, 15, 22)	X (Days 1, 15)	X (Days 1, 15)	X (Days 1, 15)	X (Days 1, 15)					

	PRE-STUDY (w/in 28 days	PRE-STUDYCycle Length = 28 days(win 28 days(+/- 3 days)					Off TX	Post
REQUIRED STUDIES	registration, unless otherwise noted)	Cycle 1	Cycle 2	Cycle 3	Cycle 4	Subsequent Cycles up to 24 Cycles	Pre- Progression FU	Progression FU
TSH, free T4, free T3 J	х							
HIV, HBV, HCV R	Х							
PT/PTT/INR L, P	X	х	Х	х	Х	X		
RESPONSE ASSESS	SMENT							
Serum β2 microglobulin, LDH, uric acid J	х							
Serum Quantitative Immunoglobulins (IgG, IgA, and IgM)	х							
SPEP with M- protein quantification	х	Х	х	Х	х	х	х	
Serum free kappa and lambda light chains	х	Х	х	Х	х	х	х	
Serum Immunofixation	х	Х	Х	Х	х	х		
Urine Protein Electrophoresis K	х	Х	Х	Х	х	х		
Urine Immunofixation Electrophoresis K	х	Х	х	Х	х	х		
Troponins (T or I) A,L	Х	Х	Х	Х	Х	X	Х	
NT-pro-BNP L	Х	X	Х	Х	Х	X	Х	
Urine or Serum Pregnancy F	x	X	Х	Х	X	X		

	PRE-STUDY (w/in 28 days	Cycle Length = 28 days (+/- 3 days)					Off TX	Post
REQUIRED STUDIES	registration, unless otherwise noted)	Cycle 1	Cycle 2	Cycle 3	Cycle 4	Subsequent Cycles up to 24 Cycles	Pre- Progression FU	Progression FU
24-hour urine A, H, K	х	X (If obtained w/in 28 days prior to C1D1, tests need not be repeated.)		х		Х	х	
Bone Marrow Aspirate or Biopsy, including FISH, Cytogenetics and Immunophenotyping	X (w/in 35 days)							
24-hour fecal fat A,G	х	X (If obtained w/in 28 days prior to C1D1, tests need not be repeated.)			X (every 3 cycles, +/- 7 days)	X (every 3 cycles, +/- 7 days)	X (every 6 months, +/- 21 days)	
X-RAYS AND SCANS	6							
Ultrasound, MRI or CT for Disease Assessment of liver, soft tissue or lymph nodes A,I	Х	X (If obtained w/in 28 days prior to C1D1, tests need not be repeated.)				X (every 6 months, +/- 21 days)	X (every 6 months, +/- 21 days)	
12-lead EKG	х	X (Days 1, 15)	х					
2D ECHO G, K	Х	X (If obtained w/in 28 days prior to C1D1, tests need not be repeated.)			X (every 3 cycles, +/- 7 days)	X (every 3 cycles, +/- 7 days)	X (every 6 months, +/- 21 days)	
SPECIMEN SUBMIS	SION							
Optional Peripheral Whole Blood, Serum. Bone Marrow Aspirate	х							

	PRE-STUDY (w/in 28 days	Cycle Length = 28 days (+/- 3 days)					Off TX	Post
REQUIRED STUDIES	prior to registration, unless otherwise noted)	Cycle 1	Cycle 2	Cycle 3	Cycle 4	Subsequent Cycles up to 24 Cycles	Pre- Progression FU	Progression FU
and Biopsy Core for Banking B								

NOTE: Forms are found on the protocol abstract page on the SWOG website (www.swog.org) and on the CTSU website (www.ctsu.org).

Forms submission guidelines are found in Section 14.0. Click here for footnotes.

NOTE Unless indicated otherwise in the protocol, scheduled procedures and assessments (treatment administration, toxicity assessment for continuous treatment, disease assessment, specimen collection and follow-up activities) must follow the established SWOG guidelines on the allowed protocol visits/treatment window as outlined in https://www.swog.org/sites/default/files/docs/2017-10/Best%20Practices%20upddate.pdf. SWOG Best Practices allows for a +/- 3 day window for 28 day cycles.

#### Footnotes for Calendar 9 (Isatuximab)

- A Tests are to be performed per Section 5.1d for suspected organ involvement. If baseline test was performed and abnormality present, the tests will be repeat until off tx prior to progression.
- B See Section 15.1.
- c Prior to treatment on each day of isatuximab, or within 3 days prior to each administration.
- E See Section 7.1c for type and screen requirements. See Appendix 18.6 for sample type and screen card.
- F For women of childbearing potential, prior to beginning treatment at each cycle (or up to 3 days prior to Day 1).
- G If required: Day 1 of Cycles 1, 4, and 7, then every 3 cycles (+/- 7 days) during treatment, then every 6 months (+/- 21 days) hematologic progression.
- H If required: Day 1 of Cycles 1, 3, 5, then every 2 cycles (+/- 7 days) until completion of treatment, then every 6 months (+/- 21 days) until hematologic progression.
-  If required: Every 6 months during and after treatment until hematologic progression, then as clinically indicated.
- J TSH with reflex to free T4, and free T3 uric acid and LDH are required only when clinically indicated; however, baseline testing is encouraged to assess for thyroid involvement, if suspected.
- K See Section 7.4 for a detailed description of organ evaluation and 24 hour urine collection assessment criteria, including serum chemistry panel requirements. All evaluations will continue at specified intervals until one of the criteria for removal from protocol treatment has been met (see Section 7.5).
- L If required: Day 1 (+/- 3 days) of each cycle.
- M See treatment plan Section 7.3.
- N See Sections 5.1d.5 and 7.1b.
- o Must include assessment of soft tissue and lymph nodes, if present at baseline; see Section 7.4e.
- P May be either INR or PT and PTT. Whichever is performed at baseline should be used throughout treatment.
- Q Assessments should continue until resolution of all acute adverse events.
- R Only required per Section 5.3 Eligibility.

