### 1.0 OBJECTIVES

#### 1.1 Primary Objective

To assess the efficacy as measured by the confirmed overall hematologic response rate (partial response or better) of isatuximab in relapsed/ refractory systemic light chain (AL) amyloidosis.

- 1.2 Secondary Objectives
  - a. To evaluate toxicities in the treatment of relapsed/ refractory AL amyloidosis with isatuximab.
  - b. To evaluate time to hematologic response.
  - c. To evaluate duration of response.
  - d. To evaluate progression-free survival (PFS).
  - e. To evaluate overall survival (OS).
- 1.3 Other Objectives
  - a. To evaluate efficacy of isatuximab in relapsed/ refractory immunoglobulin amyloid light chain (AL) amyloidosis as measured by organ specific response rates (cardiac, renal, GI, liver, soft tissue, nerve), in the subset of patients that can be evaluated for organ response.
  - b. To evaluate time to organ response in the subset of patients that can be evaluated for organ response.

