#### 10.0 CRITERIA FOR EVALUATION AND ENDPOINT ANALYSIS

10.1 Measurable disease

For the purpose of measuring hematologic response, measurable disease is defined as:

a. Positive monoclonal serum immunofixation electrophoresis or urine immunofixation electrophoresis,

and/or

- b. Serum free light chain ratio outside of normal range (normal range: 0.25 1.65)
- 10.2 Hematologic Response and Progression

Confirmation must be made by verification on two consecutive determinations.

- a. Hematologic response: (16, 17)
  - Complete Response (CR): CR is defined as laboratory values within the normal range free light chain (FLC) ratio (0.25 – 1.65) and negative serum and urine immunofixation (as per institutional laboratory values).
  - Very Good Partial Response (VGPR): A VGPR is defined as the difference between involved and uninvolved FLCs [dFLC] < 4.0 mg/dL.

  - Partial Response (PR): Partial Response is defined as a dFLC decrease of ≥ 50%, but remaining > 4.0 mg/dL
- b. Hematologic progression: 50% increase from nadir, or from baseline (if there was no response) in any ONE OR MORE of the following: *(18)* 
  - 1. Serum M-protein: 50% increase in Serum M protein to a value greater than 0.5 g/dL.
  - 2. Urine M protein: 50% increase in Urine M protein to a value greater than 200 mg/day (a visible peak must be present)
  - 3. Free light chain increase of 50% to a value greater than 10 mg/dL
- c. Stable Disease: Patients who do not meet criteria for objective response or progression (see Sections 10.2a and 10.2b) will be termed to have stable disease.
- 10.3 Organ Response (19)

Response to therapy in terms of improvement in organ dysfunction will be defined based on functional improvement in one or more involved organ systems. Only 1 parameter is required to satisfy the organ response criteria. In order to be classified as a confirmed organ response, confirmation must be made by verification on a second consecutive assessment at least 4 weeks after the first observation of response.

- a. Liver response requires either:
  - 1. A 50% decrease in (or normalization of, <1.5 IULN) alkaline phosphatase level, or
  - 2. A reduction in the span of the liver by at least 2 cm by radiographic determination.
- b. Renal response is defined as either: (20)
  - 1. A 30% decrease in urine total albumin; or

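### Alkaline phosphatase and the clinical soft-tissue exam have no scheduled assessment after isatuximab stops, so responses that depend on them can be missed or left unconfirmed

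*Combined protocol and SAP*

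**What the plan says.** Section 10.3 makes ALP a stand-alone route to liver response: "A 50% decrease in (or normalization of, <1.5 IULN) alkaline phosphatase level". The alternative route is a radiographic fall in liver span, and one parameter suffices. ALP also defines hepatic progression in 10.4a.2. For soft tissue, 10.3f accepts findings on examination or imaging, and its macroglossia examples are physical-examination findings. An organ response counts as confirmed only after a second consecutive assessment at least 4 weeks after the first.

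ALP is part of the serum chemistry panel (7.4h). In Section 9.0 that row is marked at baseline and during cycles, and footnote C times it as "Prior to treatment on each day of isatuximab, or within 3 days prior to each administration". The History and Physical row is also marked only at baseline and during cycles; footnote O says of it: "Must include assessment of soft tissue and lymph nodes, if present at baseline".

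By contrast, the row "Ultrasound, MRI or CT for Disease Assessment of liver, soft tissue or lymph nodes" has a six-monthly off-treatment entry, and its footnote I reads: "If required: Every 6 months during and after treatment until hematologic progression, then as clinically indicated". Footnote H carries its tests on as follows: "then every 6 months (+/- 21 days) until hematologic progression".

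The results serve the organ-specific response rates in 1.3a and objective 1.3b: "To evaluate time to organ response in the subset of patients that can be evaluated for organ response". Section 11.4 divides documented organ responses by patients with evaluable organ involvement at baseline, and states no assessment window.

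**The concern.** A patient can leave treatment without hematologic progression, for example through toxicity, treatment delay or completion of 24 cycles. The calendar then still provides for some organ parameters, but not for ALP or the clinical soft-tissue exam. The patient stays in the denominator for liver or soft-tissue response while the means of entering the numerator is no longer scheduled. A response first seen near the end of treatment has no scheduled second assessment. What is at stake is under-counting of these particular responses in 1.3a, and loss of late response times in 1.3b.

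**Working it through.** **1. Calendar rows side by side (Section 9.0)**

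| Parameter | Row | Off-treatment entry before progression | Row footnotes |
|---|---|---|---|
| ALP | Serum Chemistry | none | C, J, K |
| Soft-tissue/node exam | History and Physical | none | O |
| Liver span, imaged soft tissue | Ultrasound, MRI or CT | every 6 months | A, I |
| NYHA class | NYHA | yes | none |
| NT-proBNP | NT-proBNP | yes | L |
| Autonomic evaluation | Autonomic | every 6 months | A, H |
| Fecal fat | Fecal fat | every 6 months | A, G |
| 24-hour urine | Urine | yes | A, H, K |
| GI, peripheral nerve | Clinical evaluations | every 6 months | A, H, K |
| Echocardiogram | 2D echo | every 6 months | G, K |

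**2. Does the imaging row close the gap?** Only in part.

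- Liver: 5.1d.3 accepts raised ALP alone as liver involvement. Footnote A repeats a test only where it was done at baseline and was abnormal. A patient with raised ALP and a normal liver span therefore need not be re-imaged.
- Soft tissue: 5.1d.6 does not require imaging, and 7.4e makes assessment clinical. Macroglossia followed by examination has no off-treatment route.

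**3. Does footnote K remove the contrast?** K ends evaluations at removal from protocol treatment, which contradicts G and H for urine, GI, peripheral nerve and echo. The NYHA, NT-proBNP, autonomic and fecal-fat rows do not carry K. NYHA class is itself a cardiac response criterion (10.3d.2) and its row has no footnote. Some contrast remains even if K governs. Footnote L ties NT-proBNP to Day 1 of each cycle and conflicts with that row's off-treatment entry.

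**4. Uncovered time.** Inputs: 24 cycles of 28 days (7.3) and 4 years of follow-up from registration (7.7). The sum ignores delays and the short gap between registration and first dose.

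- Longest treatment window: 24 × 28 = 672 days.
- Follow-up: 4 × 365.25 = 1461 days.
- Uncovered for a progression-free completer: 1461 − 672 = 789 days; 789 / 1461 = 54%. At 30.4375 days per month this is 25.9 months, or about four six-monthly visits.
- Assumed earlier stops at 3, 6 or 12 months, progression-free to 48 months: 45, 42 or 36 months uncovered (about 7, 7 or 6 visits). These are upper limits, since earlier hematologic progression or death shortens them.
- Treatment ended by hematologic progression: no difference, because the other schedules end then too.

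**5. Confirmation.** Cycle 24 Day 1 is day 23 × 28 + 1 = 645. Day 15 is day 659, the last scheduled chemistry. An ALP response first seen on day 645 or 659 needs confirmation no earlier than day 673 or 687, when none is scheduled. One first seen at Cycle 23 Day 15 (day 22 × 28 + 15 = 631) can just be confirmed on day 659. Taking the physical exam as once per cycle, a response first seen at the Cycle 24 exam has no scheduled confirmation. The same pattern holds at any earlier stop.

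**The case against.** The strongest reply is that liver and soft tissue are not abandoned off treatment. Imaging runs every 6 months to hematologic progression, liver span alone can establish response, and soft-tissue response may rest on imaging. Section 7.4f lists imaging together with ALP, and 14.4a requests baseline radiology reports for liver or lymph-node involvement. This stands. It confines the gap to the ALP route and to disease followed only by examination.

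The other organs are also not cleanly followed to progression, given footnotes A, K and L. That stands too, and it rules out treating them as fully covered.

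Few patients may be affected. In the myeloma data of Section 2.4, progression accounted for 69 of 81 discontinuations (85%) and 73 of 85 (86%). This is only indicative for amyloidosis, but it suggests the affected group could be small. On treatment, ALP is also sampled densely: 4 + 23 × 2 = 50 scheduled times, against 12 for 24-hour urine under footnote H. Most responses during treatment should be seen.

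Section 14.4d asks for a tumor assessment form within 30 days of discontinuation, and a site could add an unscheduled ALP. But a form does not schedule a test, and 30 days need not supply a value at least 4 weeks after a first response. Capture would then depend on local practice.

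**Conclusion.** The gap is real but narrow. ALP-route liver responses and examination-only soft-tissue responses can be under-counted in patients who stop without hematologic progression, because they can be neither newly detected nor, if first seen in the last 4 weeks of treatment, confirmed on schedule. The uncovered period is 789 of 1461 days (54%) for a progression-free completer, and longer after an earlier stop. The documents do not give the number of patients with such involvement, so the effect on any response rate cannot be sized. The share of uncovered days is not the share of responses lost.

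A reader might infer that liver and soft-tissue response rates as a whole cover less patient time by construction. The documents do not support that, because the imaging row and footnote I continue to hematologic progression. Nor do they support saying that the other organs are covered for the whole pre-progression period, which requires G and H to override K and L. Section 11.4 plans no comparison between organs, so the issue is incomplete capture within these two organs.

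Organ response is an other objective (1.3). The primary and secondary endpoints are unaffected, taking progression in 10.7 as hematologic, in line with how 7.5a pairs 10.2 with 10.7. This is a cheap improvement to the calendar.

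**What to change.** In the off-treatment, pre-progression column of Section 9.0:

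- Add serum ALP for patients with baseline liver involvement, and a soft-tissue/lymph-node exam for patients with that involvement at baseline, both every 6 months (+/- 21 days) until hematologic progression.
- Add a confirmatory assessment at least 4 weeks after a response first seen at the last treatment visits.
- In the same edit, reconcile footnotes A, C, G, H, I, K and L on when organ assessments end. Footnotes C and K sit on the Serum Chemistry row and would otherwise contradict the new ALP entry. A separate ALP row would avoid this.

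The cost is calendar and footnote wording, one more analyte where blood is already scheduled for free light chains and NT-proBNP, and a brief exam where NYHA class and vital signs are already scheduled. The downside is slightly more follow-up data collection.
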